21.4. Budget Impact Analysis

A budget impact analysis to explore the cost impacts of implementation at scale will be conducted. This analysis will be developed from one previously developed for the previous HTA EMPoWER study (26). As costs at scale are directly linked to the uptake of the intervention, we will use predictions from the DCE to predict uptake rates of the intervention as delivered in the trial.

For the budget impact analysis, we will establish the costs of the proposed intervention, and the impact of making such provision available to all children who could potentially benefit. Provision to all by the NHS would inevitably lead to increased costs, however, this increased cost should be considered in the light of the potential benefits to the children, potential cost savings, and additional cost implications for other services in the public sector.

Cost data will be obtained from publicly available sources and publications, as well input from PPIE and clinical advisors. UK government datasets and related websites (e.g. Office for National Statistics (ONS), Department for Work and Pensions) will be consulted to inform population calculations. NHS data sets will be used to inform numbers of users and input to costings. Published reference sources, published research and freedom-of-information requests will be used to further inform aspects of the intervention costing, including staffing and equipment.

All of the relevant cost data will be synthesised into a tariff of NHS and non-NHS costs relating to the intervention, which will subsequently used to inform the budget impact analysis. A broad societal perspective will be taken; thus, cost implications for social care providers, other public sector resources and for the families of children requiring the interventions will be factored into the analysis.

Using this data we will model different scenarios of providing the intervention within the context of standard NHS care. We will develop hypothetical scenarios of service provision mapped on to the intervention elements and will aim to illustrate the cost of the intervention, and the potential budget impact of delivering it at scale.

22. SWAT

The trial will include two SWATs, one related to sampling methods and another related to health economics measurement. These are both established methodological uncertainties.

22.1. Sampling SWAT

The Cochrane recruitment and retention reviews (both led from Aberdeen) found very little evidence for strategies targeting under-served groups and the limited evidence available is methodologically poor. There are very few SWATs from paediatric trials, and scarcity of evidence on effective recruitment and retention in paediatric trials. The Trial Forge SWAT Network highlighted recruitment and retention of under-represented populations as a SWAT priority (https://www.trialforge.org/2024/02/a-list-of-11-priority-recruitment-and-retention-swats/. Greater inclusion of under-represented populations is also an NIHR EDI strategic and operational priority.

We will include at least one SWAT targeting recruitment of CHESS priority under-represented sub-populations (see Sampling, Section 9), most likely people experiencing socioeconomic disadvantage. Depending on the qualitative tailoring work coming from our 6-month set-up and tailoring phase, we may include a second SWAT evaluation. Examples interventions could be video-based or interactive layered participant information provision. By layered we mean explicitly understanding and delivering the information that is most important to participants, which may vary by participant group, allowing them to regulate the level of detail they want. Use of video is a priority coming from the SWAT Network prioritisation work because videos are already being used despite limited evidence to support or refute their use, they offer the potential to better support individuals with lower literacy and may work better for some ethnic groups that prefer

verbal over written information. Key to our SWAT design is use of the INCLUDE Socioeconomic Disadvantage and Ethnicity Frameworks and stakeholder-informed content development, both of which will come from the set-up and tailoring phase. The measured outcomes will be recruitment, retention and cost.

We will share our protocol(s) both through the Belfast SWAT Repository and with the York Trial Forge SWAT Centre to support potential replication in other host trials they work with.

22.2. Targeted sampling SWAT

The first sampling SWAT intends to determine if targeted sampling approaches increase the number of children living in socioeconomically disadvantaged areas who take part in trials.

This SWAT will evaluate alternative ways of trying to ensure that children living in socioeconomically disadvantaged areas are well-represented with the CHESS population. Living in socioeconomically disadvantaged areas means living in areas of the UK with postcodes that fall into deciles 1 to 4 inclusive of the Index of Multiple Deprivation (IMD), or its equivalent depending on which nation within the UK a person is living.

When the SWAT is implemented, clusters will be randomised either to simple random sampling (our standard approach), as detailed in section 9.3 (control) or targeted sampling (intervention). Randomisation will be stratified by allocation group. Within each allocation group, block randomisation will be carried out to ensure equal allocation.

For targeted sampling, the cluster PI, or their delegate, will identify and make available the full, non-identifiable caseload list of potential participants to CHaRT at the central trial office. This list will consist of a non-identifiable ID and a postcode for the child. This anonymised table of information will be provided in an excel file format (or similar) using a secure file transfer system (such as a password protected encrypted file/ZendTo). The trial statistician will import the tables to STATA v18 for targeted sampling. Appropriate tools will be used to obtain deprivation data for the postcodes provided by the sites. Eligible children living in IMD 1 to 4 areas will be given preference to be invited to take part in CHESS ahead of children living in IMD 5 to 10 areas. In order to do this, a dummy variable called IMD_cat will be generated where IMD 1 to 4 will be coded as 1 and IMD 5 to 10 will be coded as 2. The data will be split by IMD_cat and saved into two datasets (IMD1 and IMD2). A random number using runiform() in STATA will be generated and assigned to children in both the datasets separately. The list will be sorted by the assigned random numbers in both the datasets. Using the IMD1 dataset, IMD2 dataset will be appended which will result in children in IMD1 dataset at the top of the list and IMD2 at the bottom of the list. We will then generate a dummy variable called *n* to number the participants from the first child to the last child in the list. A table which includes unique code, postcode, IMD and n which has been generated will be exported into excel file. A verification process checking for duplicates or errors in the selection process will be carried out. The trial statistician will send the excel file back to the Pl/delegate using a secure file transfer system (such as ZendTo). The Pl/delegate will invite the parents of the sampled children to participate in data collection in CHESS, beginning with the randomly assigned first child on the list and continue through the list until the cluster target sample of 24 parents have agreed to participate in the data collection and follow up in CHESS, or the full list exhausted. The cluster PI will receive guidance from the research team as required.

The details of the sampling process will be recorded including the date, method used, and any issues encountered. A copy of the list will be maintained in University of Aberdeen secured network drive.

22.3. Health economics outcome measurement SWAT

While all the health measures we propose to use have been intensively tested and are widely used across populations (with some of the measures being evaluated in thousands of studies in different populations to date), evidence of their psychometric properties in the context of trials in the present population is limited. This specific SWAT will aid interpretation of the findings of this trial, but also support researchers in the design of future trials in this or similar participant groups.

As part of this SWAT, we will assess the basic measurement and psychometric properties of the health economic measures (CHU9D, SF-36, and ICECAP-CES) at 12-month follow-up; 12 month data will be used as baseline measures are taken prior to cluster randomisation. Assessment will include the percentage of completed measures with missing data; floor/ceiling effects; test-retest reliability; convergent/divergent validity; agreement and known-group validity

Test-retest evaluation will require re-administration of the 12-month measurements 2 weeks after initial data collection, and will be collected from a 20% subset (n= 192) of total participants. Similarly to the DCE (section 21.3) we will select a subset of intervention and control clusters to undertake test-retest measurements, these clusters will be separate to the DCE clusters to ensure participants are not unduly burdened with data collection.

Provisional measurements of percentage of completed measures with missing data will be evaluated following baseline and 6-month period of the pilot trial, to highlight any data collection issues, with full SWAT evaluation completed after 12-month data collection for the full trial.

Primary subgroups (control and intervention) and secondary subgroups (sex, mobility, and socioeconomic deprivation) will also be evaluated for percentage of completed measures with missing data, floor/ceiling effects and test-retest reliability.

We will pay specific attention to evaluation of the CHU9D, as work is ongoing in validating it for children in our target age group.

We will examine correlation and agreement between outcome measures using assessment of construct validity (i.e. convergent/divergent validity) and Bland-Altman plots of agreement. These assessments will be undertaken to determine the extent to which these tools are measuring the same underlying constructs and are in sufficient agreement to be used interchangeably to measure the same construct. We will undertake known-group validity assessment to examine the ability of these measures to distinguish distinct groups where we would expect to observe differences between specific groups.

23. Trial management and oversight

The trial will be led by an expert, multidisciplinary team and will be run under the auspices of the Centre for Healthcare Randomised Trials (CHaRT), a fully registered UK Clinical Research Collaboration Clinical Trials Unit based in the University of Aberdeen. CHaRT has internationally recognised expertise in the design, conduct, analysis, and reporting of multicentre trials and has significant experience in Cluster RCTs. Sheffield Children's Trust will host the clinical allied health lead (SA) and be study Sponsor; and Newcastle University will host the CI ([name]) who has worked closely with both the Aberdeen and Sheffield colleagues, and with all study Co-Is, on previous projects. A Project Management Group (PMG), an independent Trial Steering Committee (TSC) and an independent Data Monitoring Committee (DMC) will be convened.

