8.2. Target patient population: description, inclusion, exclusion

The target patient population is children with neurodisability with or without a defined clinical diagnosis, from age 12 months to 4 years 6 months (at time of sampling the child), where self-care support is indicated either on the referral or clinical assessment, together with one of the child's parents or carers. Neurodisability refers to the established consensus definition,³ and covers a range of children typically seen in paediatric community/outpatient care. For the child's age, the upper limit cut off is based on estimated age of school entry, where school entry is the significant developmental transition recommended by our PPIE.²

Inclusion criteria:

- Any child with neurodisability;³
- age at least 12 months and not older than 4 years 6 months on the date of sampling the child;
- seen by at least one paediatric community/outpatient therapy service; where self-care support is indicated;

- where the family and therapist agree on a need for self-care intervention;
- who has been randomly sampled for data collection from the participating therapists' caseloads;
- AND whose parent is willing to consent to data collection and comply with study procedures.

No restriction is placed on child mobility, cognitive or communication capacities and due to the nature of caseloads and random sampling of children we anticipate the same to include a mix of children across capacities.

Exclusion criteria:

- Children with no neurodisability;
- with only sensory impairment (e.g. visual, hearing);
- with degerative condition(s);
- no clear self-care problems or goals;
- receiving one-off advice and discharge only;
- hospitalised or in end-of-life care at the point of sampling;
- and/or a sibling already taking part in (i.e. providing data to) the CHESS trial.

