9.2. Identifying eligible caseloads and sampling children

Before site/cluster randomisation, the local NHS organisation cluster PI (or a person designated by them), who already has access to the relevant child data, will identify their local caseload (sampling frame) of eligible children. The cluster PI, or their delegate will then collate a non-identifiable list of relevant caseloads within that cluster. That is, lists that consist of children from 12 months to 4 years 6 months old, with neurodisability, with likely self-care problems.

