15.1. Assessing outcomes

Assessment will be at baseline and at 6, 9 and/or 12 months after the therapy team has been trained in the intervention (Table 2, below). Further details about collection of outcome data are provided elsewhere in this section.

| Table | 2: | Timing | of | data | collection |
|-------|----|--------|----|------|------------|
|-------|----|--------|----|------|------------|

| Outcome | Baseline | 6 months | 9 months | 12 months |
|---------------------------|----------|----------|------------|-----------|
| Baseline CRF ¹ | Х | | | |
| Harms | | Х | | Х |
| Accidents during the | | | | |
| powered mobility | | | Throughout | |
| sessions ² | | | | |
| Unplanned attendance | X | Х | | Х |
| at hospital | | | | |
| PEDI-CAT | Х | X X | | X X |
| Vineland-3 coping | Х | Х | | Х |
| skills subdomain | | | | |
| CHU9D (proxy | X | Х | | Х |
| version) | | | | |
| SF-36v2 | Х | Х | | X |
| ICECAP CES | X | Х | | Х |
| CHU9D, SF-36, and | | | | Х |
| ICECAP CES 2week | | | | |
| test/retest | | | | |
| Satisfaction with | | | | Х |
| treatment | X | X | | X |
| Health Service Use | X | Х | | X |
| Questionnaire (SUQ) | | | | |
| DCE (sub-set of | | | X | |
| participants) | | | N N | |
| Time and travel | | | X | |
| questionnaire | | | | V |
| Case note | | | | X |
| review/follow up CRF | | | | |

¹Completed by local cluster team at baseline, ²Local cluster team will provide DATIX (or similar) reports of any accidents during the powered mobility sessions

Based on our previous longitudinal study of 300 children (1-5yrs) across 13 NHS organisations, with data collection every 6 months, we anticipate >90% of parents will prefer to complete the questionnaires over the phone or online, with high levels of flexibility required to accommodate around family routines (e.g. evenings, weekends, lunch breaks). PPIE has further emphasised that: helping parents to understand the trial and the context in which questionnaires are used matters; and having a trusted relationship with the trial team and a sense of being heard is important. We have previous experience of successful longitudinal study protocols of multiple questionnaires with this population; and will further build on this in the 6-month pre-trial set-up and tailoring period.

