15.2. Baseline

Participating parents will complete the baseline questionnaire after consent and prior to cluster randomisation, including child and parent ethnicity and sociodemographics. The local cluster team will complete the baseline CRF including information on child age and diagnoses.

At baseline, we will also collect contact details of participating parents (including postal address, email, home and mobile number) and their contact preferences (email, phone call, post - and where required as a method of adapted participation to support inclusion, in-person visits).

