15.3. Follow-up

The vast majority of the parent reported outcomes will be collected at baseline, 6, and 12 months post-randomisation, using questionnaires completed at home using their preferred method of completion (phone, post, email or in-person). The primary outcome measure (PEDI-CAT) uses computer adapted testing, which means it cannot be completed on paper. The questionnaires will include PEDI-CAT, SF-36v2, CHU9D, Vineland 3 Coping Skills Subdomain, and questions about current and recent treatment, satisfaction with treatment and harms. First reminders will be issued to participants (according to their stated contact preference). If there is no response, up to two follow-up reminders (according to their stated contact preference) will be attempted – with at least one of these via text message to allow for a change of postal / email address. Test-retest evaluation will require re-administration of the 12-month measurements 2 weeks after initial data collection, and will be collected from a 20% subset (Target Sample Size = 192, see section 22.5 for selection methods) of total participants. The Discrete Choice Experiment (DCE) and Time and Travel questionnaire (TTQ) will be collected at approximately 9 months post-randomisation only, with the DCE being completed by a sub-set of the respondents only (Target Sample Size = 240, see section 21.3 for selection methods).

Questionnaires will be administered to all parents consented for data collection, regardless of adherence with treatment, unless they have opted out of questionnaire follow-up. This means that consented parents and children who have not received their allocated treatment, have received the non-allocated treatment, or where therapy has been discontinued, will continue to be followed up in the study.

If questionnaires are returned as non-deliverable, attempts will be made by the local cluster team or staff at the Trial Office to trace the participant. In case of non-return of questionnaires, attempts are made by local cluster staff or staff at the Trial Office to trace the participant directly, and/or indirectly by contacting the GP.

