Health Related Quality of Life (HRQoL) will be calculated using a variety of measures. For the child, HRQoL will be measured using the proxy version of the CHU-9D.⁴¹ This is currently validated for children ≥5-years-old, however a proxy version with additional guidance is available for children under 5. Recent evidence from Australia⁴¹ concluded that the measure was found to be valid and reliable to measure HRQoL in children aged 2–4 years. As there is currently no evidence on the validity and reliability of the proxy CHU-9D for children under 2, we will conduct a sensitivity analysis which excludes those children aged under 2 at baseline from the analysis sample. For the parent carers, HRQoL will be measured using the SF-36v2. To further assess the parent carer's care-related quality of life, ICECAP Carer Experience Scale (CES) will also be collected. This tool focuses on 'care-related quality of life' rather than health-related quality of life, comprising attributes that are pertinent to unpaid carers.

In the base case analysis QALYs will be based on responses to the CHU9D (child) and the SF-6D, derived from response to the SF-36 (parent carer). QALYs for each participant will be obtained by scoring responses to the two tools at baseline, 6, 12 months post randomisation using scoring systems available at the time of analysis that are appropriate to each tool. QALYs cannot be calculated for the CES. The mean CES index at each data collection point will be estimated, with this information used to complement the QALYs calculated from the SF-6D in the CCA.

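### The health economics measurement SWAT (section 22.3) assesses the validity and reliability of CHU9D only at 12 months, when every child is at least 2, so the age band that section 21.1 says lacks evidence is not covered

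*Protocol*

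**What the plan says.** Section 22.3 plans to assess missing data, floor/ceiling effects, test-retest reliability, convergent/divergent validity, agreement and known-group validity for CHU9D, SF-36 and ICECAP-CES, all at 12-month follow-up. The reason given is that "12 month data will be used as baseline measures are taken prior to cluster randomisation". One exception is planned: a provisional look at the percentage of measures with missing data after the baseline and 6-month waves of the pilot. The subgroups named are trial arm (primary) and sex, mobility and deprivation (secondary); child age is not among them. On CHU9D the section says: "We will pay specific attention to evaluation of the CHU9D, as work is ongoing in validating it for children in our target age group".

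Section 8.2 defines that age group at entry: "age at least 12 months and not older than 4 years 6 months on the date of sampling the child". Section 21.1 cites evidence supporting the proxy CHU9D at ages 2 to 4, and then says: "As there is currently no evidence on the validity and reliability of the proxy CHU-9D for children under 2", a sensitivity analysis will leave out children who were under 2 at baseline. The base case uses CHU9D scores at baseline, 6 and 12 months for all children.

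**The concern.** The protocol itself identifies children under 2 as the group in whom the child utility measure is untested, and it runs a sub-study that singles out this measure for attention in an age group starting at 12 months. It then fixes the sub-study's assessments at a wave by which every child has left the untested band. The scores given below age 2 would feed the base-case child QALYs with no evidence from the trial on how the measure behaves at that age, although the data needed for much of that evidence are collected.

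The stated reason does not justify this. Floor and ceiling effects, correlation with other measures and separation of known groups can all be examined in participants who have not yet been allocated. Data from before randomisation are also free of any treatment effect and of the drop-out of about 15% assumed in section 18.1. The reason does not touch the 6-month data at all, since these are collected after randomisation.

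**Working it through.** **Inputs from the protocol**
- Age on the date of sampling: 12 to 54 months (section 8.2).
- Order of events: caseloads are identified (section 9.2) and sampled parents receive their packs (section 10.3.2) before cluster randomisation. For baseline, section 15.2 says: "Participating parents will complete the baseline questionnaire after consent and prior to cluster randomisation".
- Timing of follow-up: section 15.3 says "The vast majority of the parent reported outcomes will be collected at baseline, 6, and 12 months post-randomisation"; section 15.1 says "Assessment will be at baseline and at 6, 9 and/or 12 months after the therapy team has been trained in the intervention". Section 14.1 counts from the start of the intervention and section 20 from recruitment.
- Total sample: 960. Retest subset: 20%, n = 192 (section 22.3).

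**The plan's own figure.** 0.20 × 960 = 192, which reproduces the retest subset.

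**Age at each wave.** Sampling precedes recruitment, randomisation, training and the start of the intervention. Age at a wave is therefore at least age at sampling plus the months counted to that wave:
- baseline: from 12 months;
- 6 months: from 12 + 6 = 18 months;
- 12 months: from 12 + 12 = 24 months.

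On nominal timings, the number of children under 24 months at the 12-month wave is 0 of 960 under any of the four origins. The 2-week retest comes later still.

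**Children under 2 at the earlier waves.** The protocol gives no age distribution for its sample, so this part rests on an assumption. It also ignores attrition and the short gap between sampling and baseline. With ages uniform over 12 to 54 months:
- baseline: (24 − 12)/(54 − 12) = 12/42 = 0.286; 0.286 × 960 ≈ 274;
- 6 months (under 18 months at sampling): (18 − 12)/42 = 0.143; 0.143 × 960 ≈ 137.

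A younger sample raises both shares. As an illustration only, a normal distribution with the mean of 21 and SD of 8 months reported for ActiveCHILD in section 11.2, truncated to 12 to 54 months, gives 0.593 (about 569) at baseline and 0.257 (about 247) at 6 months. ActiveCHILD is a weak guide to age here. The protocol uses it as a benchmark for inclusion, its target table has no row for age, and 118 of its 301 families are described as recruited through specialist services.

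**Where scores from under-2s are used.** They enter the base-case QALYs (section 21.1). In the SWAT, their only use is the provisional missing-data percentage in the pilot, which is not split by age.

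**What an earlier analysis would need.** Table 2 shows CHU9D, SF-36v2, CES, Vineland-3 and PEDI-CAT all collected at baseline and 6 months. Section 15.2 puts child age and diagnoses on the baseline CRF.

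**The case against.** The best defence has four parts.

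First, section 21.1 already responds to the lack of evidence under 2 with a sensitivity analysis, and section 21 makes a cost-consequence analysis the main economic output, so the conclusions do not hang on child QALYs alone. This stands as a limit on the harm. It does not close the gap: dropping those children shows whether the result moves, not whether their scores are valid, so it cannot say which result to believe if the two differ.

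Second, arm is the SWAT's primary subgroup for missing data, floor/ceiling effects and test-retest, and a comparison by arm needs data from after randomisation. This stands, and is a good reason to keep the 12-month analyses. It is no reason to omit an earlier one.

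Third, results at age 2 and over are worth having. The support that section 21.1 cites at ages 2 to 4 is not described there as coming from children with neurodisability, so the 12-month analyses are not redundant. This stands too.

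Fourth, CHU9D is collected at the earlier waves anyway, so nothing is lost for good, and section 21 leaves detail to a Health Economics Analysis Plan that is not at hand. However, section 22.3 itself fixes the time point and gives the reason, so the wording to correct is in the protocol.

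Three stronger readings are tempting. A reader might infer that the SWAT uses 12-month data alone; the provisional missing-data check in the pilot uses baseline and 6-month data, when children under 2 can be present. A reader might infer that the protocol breaks a promise to validate CHU9D under 2; it promises attention to the target age group, most of whose range is 24 months or older, and nowhere expressly undertakes validation below 2. A reader might extend the point to all three measures; SF-36v2 and CES describe the carer, so the child-age argument does not apply to them.

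**Conclusion.** The point holds as a mismatch between the SWAT's stated focus and the time point chosen for it. No floor/ceiling, reliability, convergent/divergent, agreement or known-group assessment of CHU9D will include a child under 2. That zero follows from the protocol's own entry age and timings, provided the stated order of sampling before randomisation is followed.

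The number of children whose earlier scores go unexamined is less certain: about 274 of 960 (29%) at baseline under uniform ages, and more if the sample is younger. The higher illustrative figure should not be taken as an estimate.

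The consequence is confined to a secondary sub-study and to the interpretation of the child QALYs. The primary outcome, power and trial conduct are untouched.

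**What to change.** In section 22.3, keep the 12-month analyses, the comparisons by arm and the 2-week retest as planned. Then:

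- Add completeness, floor/ceiling, convergent/divergent and known-group analyses of CHU9D on the baseline data, presented by age band (12 to 23 months; 24 months and over).
- Repeat them on the 6-month data for children still under 2 at that wave.
- Use baseline SF-36v2 and CES only as comparators, if they are wanted for the convergent/divergent analysis.
- Reword the reason for the time point, so that it explains the use of 12-month data for comparisons by arm and no longer reads as ruling out earlier data.
- State that test-retest reliability under age 2 remains unassessed, because the only retest is at 12 months.

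The cost is a change to the SWAT wording and a few more tables from data already scheduled, with no added burden on families. The known-group analyses depend on the grouping variables being recorded at the wave used.

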14.2. Secondary outcome measures

The choice of secondary outcomes has been informed by the requirements of the commissioning brief, and PPIE and wider stakeholder advice.

- Self-care involvement within dynamic child-caregiver interactions at baseline, 6 months and 12 months, with focus on the child's agency, comfort, stress, psychological safety, measured using the Vineland-3⁴⁰ coping skills subdomain.
- Child health related quality of life: given the age of children we will use the proxy version of the CHU9D, at baseline, 6 and 12 months.⁴¹ A version of this has been developed suitable for pre-school children
- Caregiver health: SF-36v2⁴², at baseline, 6 and 12 months. Chosen to capture health impacts on carers and allow the calculation of QALYs
- Carer care-related quality of life at baseline, 6 months and 12 months: ICECAP Carer Experience Scale (CES).⁴³ Chosen to capture aspects of carer quality of life beyond health likely to be affected by the intervention
- Potential risks and harms, including physical injury for the child and parent and other potential harms,⁴⁴ identified via the harms reporting process (section 16) and process evaluation
- Satisfaction with treatment, identified via the 12 month questionnaire and process evaluation
- Health and social care service use: collected via a service use questionnaire (SUQ). Developed through public and stakeholder involvement
- Cost for carers/families for accessing services and purchased care: Using an SUQ and a time and travel Questionnaire (TTQ) (TTQ developed through public and stakeholder involvement)

The subsections of these tools cover the most common important child health indicators across existing paediatric core outcome sets,⁴⁵ including pain, communication, social interaction, and mobility. Data on the children's diagnoses will be extracted from clinical notes.

15. Data collection and processing

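### Section 22.3 plans Bland-Altman plots between CHU9D, SF-36 and ICECAP-CES to judge interchangeability, but no two of these measures share both the person described and the construct

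*Protocol*

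**What the plan says.** The health economics measurement SWAT (section 22.3) names three instruments and no others: "we will assess the basic measurement and psychometric properties of the health economic measures (CHU9D, SF-36, and ICECAP-CES) at 12-month follow-up". It lists missing data, floor and ceiling effects, test-retest reliability, convergent/divergent validity, agreement and known-group validity. Agreement is thus an item separate from test-retest reliability.

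The method for agreement is then given: "We will examine correlation and agreement between outcome measures using assessment of construct validity (i.e. convergent/divergent validity) and Bland-Altman plots of agreement". The stated purpose is to find out how far the tools capture the same construct and whether they "are in sufficient agreement to be used interchangeably to measure the same construct". No pairs, no common scale and no threshold for sufficient agreement are given.

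Section 21.1 defines what each instrument is for:
- CHU9D: "For the child, HRQoL will be measured using the proxy version of the CHU-9D".
- SF-36v2: "For the parent carers, HRQoL will be measured using the SF-36v2".
- CES: it addresses care-related quality of life "rather than health-related quality of life, comprising attributes that are pertinent to unpaid carers".

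Section 14.2 gives the reason for including the CES: "Chosen to capture aspects of carer quality of life beyond health likely to be affected by the intervention". Section 21.1 adds that "QALYs cannot be calculated for the CES" and that the CES index complements the SF-6D QALYs. The opening of section 21 says that child and carer impacts cannot be combined under current methods, which is one reason for choosing a cost-consequence analysis.

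**The concern.** Bland-Altman limits describe measurement disagreement when two methods measure the same quantity, in the same subject, in the same units. Sections 14.2 and 21.1 chose these three instruments because they cover different people or different constructs. An interchangeability aim runs against the reasons given for collecting them.

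If the text is followed, wide limits could mean a poor instrument, a carer whose health differs from the child's, or a carer whose caring experience differs from their health. The plot cannot tell these apart. Rescaling the scores to a common metric would not help, because part of what the plot then shows would come from the rescaling.

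The stake is modest but real. Section 22.3 says the SWAT will aid interpretation of this trial and support the design of later ones, with specific attention to CHU9D. Section 31.1 commits to publishing it because methods for assessing quality of life in young children are little studied. A comparison of CHU9D with carer scores for agreement says nothing about how well CHU9D measures the child.

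**Working it through.** **1. The only figure in section 22.3.** Test-retest subset: 20% of 960 = 0.20 × 960 = 192. This reproduces the stated 192. The between-measure agreement analysis carries no figure.

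**2. Person and construct for each instrument (sections 14.2 and 21.1).**

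| Measure | Person described | Construct |
|---|---|---|
| CHU9D (proxy) | Child | Health-related quality of life |
| SF-36v2 | Parent carer | Health-related quality of life |
| ICECAP-CES | Parent carer | Care-related quality of life, distinguished from health-related |

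**3. The three possible pairs.**
- CHU9D and SF-36: different person.
- CHU9D and CES: different person and different construct.
- SF-36 and CES: same person, different construct.

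No pair matches on both. CHU9D and SF-6D utilities could be placed on one utility-type scale, but their difference would be child health minus carer health, not measurement disagreement.

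**4. What the plots would show.** The half-width of the 95% limits is 1.96 × √(s₁² + s₂² − 2·r·s₁·s₂). The protocol gives neither SDs nor between-measure correlations, so the values below are assumptions.

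*Both scores standardised to SD 1.* The half-width becomes 1.96 × √(2(1 − r)):
- r = 0.1: 1.96 × √1.8 = 2.63 SD
- r = 0.3: 1.96 × √1.4 = 2.32 SD
- r = 0.5: 1.96 × √1.0 = 1.96 SD
- r = 0.7: 1.96 × √0.6 = 1.52 SD

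Solving for r with half-width w gives r = 1 − (w/1.96)²/2. Limits within ±1 SD need r of about 0.87, and within ±0.5 SD about 0.97. Correlations that high are hard to expect between a child score and a carer score. Standardising also sets the mean difference to zero, so an apparent absence of bias would be produced by the scaling.

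*Raw scores in different units.* With assumed SDs of 0.15 and 15 and r = 0.3: 1.96 × √(0.0225 + 225 − 1.35) = 29.3. The half-width lies between 29.3 and 29.4 for any r from 0 to 0.5, and the difference correlates about −1.0 with the mean. The plot then shows the difference in units and little else.

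*One scale, unequal spread.* With assumed SDs of 0.15 and 0.10, the difference correlates 0.39 to 0.43 with the mean for r from 0 to 0.5. This would look like proportional bias but comes only from the unequal SDs.

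**The case against.** The sentence in section 22.3 poses a question: how far do the tools capture the same construct? A negative answer is permitted, and Bland-Altman is paired with convergent/divergent validity, so the two would be read together. That is fair. Convergent/divergent correlations can address the question. A Bland-Altman plot between these instruments adds nothing to the answer, because its differences are not measurement disagreement whichever way they fall.

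The operational detail may lie elsewhere. Section 21 defers the health economics analyses to a separate analysis plan, section 22.1 mentions SWAT protocols to be shared, and section 31.1 mentions registration. None is at hand, and the choice of scores to plot is properly left to such documents. But the point is not missing detail. The protocol states a method and an aim that do not fit the tools it names, and a later plan that follows them inherits the mismatch.

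A reader might infer three stronger things that the protocol does not support.
- *That all three measures describe different people.* This is true only of CHU9D against the two carer measures; SF-36 and CES both describe the carer.
- *That the whole SWAT is uninterpretable.* Only the agreement element is affected. Missing data, floor and ceiling effects, test-retest reliability, convergent/divergent correlations and known-group validity remain sound.
- *That a finding of non-agreement is fixed in advance.* The correlations above are assumed, the protocol sets no threshold that the limits could fail, and rescaling could even produce apparent agreement.

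**Conclusion.** The concern holds for the cross-measure Bland-Altman and interchangeability element of section 22.3. By the protocol's own definitions, no pair among CHU9D, SF-36 and CES shares both person and construct, so limits of agreement between them cannot separate poor measurement from a different person or construct. This conclusion rests on sections 14.2, 21.1 and 22.3 and does not depend on any assumed number.

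The size is illustrative only: limits of about ±2.6 to ±2.0 SD on standardised scores for assumed correlations of 0.1 to 0.5, with no stated agreement limit to judge them against.

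The matter is minor. One of the six listed components of a methodological sub-study is affected. The primary outcome, the trial's sample size, the QALY derivation and the cost-consequence analysis are untouched.

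**What to change.** In section 22.3:
- Delete the aim of judging whether CHU9D, SF-36 and CES are interchangeable, and delete the between-measure Bland-Altman plots.
- Keep the convergent/divergent correlations between measures, with the expected direction for each pair stated before the 12-month data are analysed.
- Apply Bland-Altman to each measure against its own 2-week retest, where person, construct and scale are the same. The retest is already planned in 192 participants.

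Any health economics analysis plan or SWAT protocol should be aligned with the revised text. The cost is a change of wording, with no new data and no added burden on families.
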